15.3 Foreseeable Adverse Events and Anticipated Adverse Device Effects

Risks associated with stenting using the ABT NG DES 48, together with their likely incidence, are described in the IFU and **Appendix IV**.

For all general risks associated with stenting/PCI procedures using DES/everolimus stents, risks conferred by the ABT NG DES 48 are anticipated to be similar to or less than overlapping stent treatment for the same total stent treatment length. Because of the long stent length, there are a few considerations specifically related to the use of the ABT NG DES 48, which are addressed below.

- **Total drug dose:** Although the longer length of individual ABT NG DES 48 results in a greater total amount of everolimus drug than the currently approved individual XIENCE family of stents with shorter lengths, data from the preclinical maximum dose studies and human pharmacokinetic study support that there are no systemic or vascular safety concerns associated with the total amount of drug on single, or even multiple, ABT NG DES 48 stents.
- **Device deliverability:** The ABT NG DES 48 delivery system utilizes the same principle of operation and materials that are currently in use by the other XIENCE family of coronary stent systems with shorter stent lengths. The deliverability was not affected by the long stent length. Bench testing using a Synthetic Arterial Model (SAM) has demonstrated that the performance of the ABT NG DES 48 satisfies the deliverability design goals, which were set to be similar to the performance of the commercially available 38 mm XIENCE family of stent systems.
- **Vessel taper:** Only a small amount of additional vessel taper is anticipated to be encountered with ABT NG DES 48 than is currently treated with the commercially available and widely used 38 mm XIENCE family of stents due to the incremental 10 mm length between the two stent sizes. The common practice of sizing stents to the distal vessel diameter and the maximum stent dilation limits are only slightly increased (from 5.5 mm to 5.75mm) as those provided in the current XIENCE family of stents' Instructions for Use (IFU). Abbott believes that these practices provide guidelines for safe use of the ABT NG DES 48 with regards to vessel taper.
- **Side branch jailing:** Side branch jailing is a general risk associated with stenting. The likelihood of side branch jailing with a 48 stent is not anticipated to be inherently different than the likelihood of side branch jailing with the same total stent length comprised of multiple overlapping stents. In fact, areas of two layers of metal created by overlapping stents may increase the risk of side branch jailing, and the use of ABT NG DES 48 can avoid stent overlap and help reduce this risk. Hence, Abbott believes that the ABT NG DES 48 will have the same overall likelihood of, and possibly lower overall risks related to, side branch jailing as compared to the same total stent length comprised of multiple overlapping stents.

Below are other risks associated with the coronary angiography, which is an integral part of the PCI procedure. These risks are not specific to the ABT NG DES 48 and may happen with any angiography procedure for heart vessels:

- Exposure to radiation
- Heart attack, stroke
- Injury to the catheterized artery
- Irregular heart rhythms (arrhythmias)

Clinical Investigation Plan

- Allergic reactions to the dye or medications used during the procedure
- Kidney damage
- Excessive bleeding
- Infection

There may be risks related to the device under investigation that are unknown at present. Likewise, the exact frequency of the risk may be unknown.

15.4 Residual Risks Associated with the Device Under Investigation, as Identified in the Risk Analysis Report

Residual risks are risks remaining after protective measures per Abbott's risk management process have been applied or taken. The residual risks to the subject were identified from literature review or the complaint data review of the current commercially available XIENCE family of stents.

15.5 Steps Taken to Control or Mitigate Risks

In-depth recommendations, special precautions and instructions regarding subject selection, device handling, device placement and system removal are included in the IFU.

Risks associated with the use of the ABT NG DES 48 during this clinical study are minimized through device design, investigator selection and training, pre-specified subject eligibility requirements, study monitoring to ensure adherence to the protocol and the use of a DSMB.

These risk management aspects are detailed below:

Device Design: the design of the ABT NG DES 48 includes many features aimed at minimizing potential risks. The major safety features of the device are described below:

- The stent size matrix includes longer lengths to enable better size matching between target vessel and implant.
- The initial degradation rate has been maintained relative to the predecessor to maintain vessel support until full tissue coverage has been achieved.
- The drug everolimus and drug dose density are the same as the predecessor.
- The ABT NG DES 48 is constructed from well-characterized, biocompatible materials that have undergone extensive testing.

Investigator Selection and Training: It is also stated in the IFU that the devices can only be used by physicians who have received appropriate training on how to use the device. This statement is interpreted to mean that the physician users are expected to be aware of the known and foreseeable safety risks associated with the use of the devices including the surgical and/or non-surgical treatment of these conditions.

- Only physicians who are skilled in the manipulation of catheter-based technology in the vasculature and heart and have a good understanding of the risks associated with these manipulations, will be selected as investigators for this trial.
- Emergency surgical back-up should be available as per the institution's standard procedures.

Clinical Investigation Plan

- The Sponsor will be available to provide technical support to answer questions regarding the function of the ABT NG DES 48.
- Pre-specified subject eligibility requirements - as stated in Section 5 of the protocol.

Ensuring strict adherence to the clinical investigation protocol

The clinical investigation will be carefully monitored by the Sponsor monitor (or designee) to ensure adherence to the Clinical Investigational Plan. Adverse events and device deficiencies will be reported to Abbott/designee and will be monitored internally for safety surveillance purposes. A DSMB will be used for the study.

15.6 Risk to Benefit Rationale

The foreseeable rates of the anticipated adverse events associated with the procedure and implantation of ABT NG DES 48 are all below 10% (see **Appendix IV**). Moreover, as detailed in **Section 15.2**, there is an unmet need for treatment of coronary long lesions, with limited options currently available. Taking these into consideration, the clinical benefit that may be expected from treatment of coronary long lesions with the ABT NG DES 48 outweigh the possible risks that subjects may experience when participating in this trial.

17.0 APPENDIX I: ABBREVIATIONS AND ACRONYMS

Acronym or Abbreviation	Complete Phrase or Definition
%DS	percent diameter stenosis
ACC/AHA	American College of Cardiology/American Heart Association
AE	adverse event
AMI	acute myocardial infarction
ARC	Academic Research Consortium
BBB	bundle branch block
BMS	bare metal stents
CABG	coronary artery bypass graft
CAD	coronary artery disease
CCG	Cockcroft-Gault equation
CEC	Clinical Events Committee
CI	clinically-indicated
CIP	clinical investigation plan
COVID-19	coronavirus disease 2019
CK-MB	creatinine kinase myocardial-band isoenzyme
CT-FFR	computed tomography-fractional flow reserve
CTO	Chronic total occlusion
DD	device deficiency
DES	Drug-eluting stent
DM	device malfunction
DSMB	Data Safety Monitoring Board
DMR	death, MI, and revascularization
EC	Ethics Committee
ECG	Electrocardiogram
eCRF	electronic case report form
EDC	electronic data capture
EECS	everolimus eluting coronary stent
EECSS	everolimus eluting coronary stent system
FAS	full analysis set
FDA	Food and Drug Administration

Clinical Investigation Plan

Acronym or Abbreviation	Complete Phrase or Definition
GCP	Good Clinical Practice
GFR	Glomerular filtration rate
HIPAA	Health Insurance Portability and Accountability Act
ICF	Informed Consent Form
IDE	Investigational Device Exemption
IFU	Instructions for Use
iFR	Instantaneous wave-free ratio
IRB	Institutional Review Board
KM	Kaplan-Meier
LAD	left anterior descending coronary artery
LBBB	left bundle branch block
LCX	left circumflex coronary artery
LVEF	left ventricular ejection fraction
LVH	left ventricular hypertrophy
MDRD	Modification of Diet in Renal Disease
MedDEV	Medical Devices Directives
mg	milligram
MHRA	The Medicines and Healthcare Products Regulatory Agency
MI	myocardial infarction
mL	milliliter
mm	millimeter
N	sample size; also N
NHLBI	National Heart, Lung, and Blood Institute
NSTEMI	Non ST-Elevation MI
NQMI	non-Q wave myocardial infarction
OCT	optical coherence tomography
OUS	Outside of United States
PBMA	poly (n-butyl methacrylate)
PCI	percutaneous coronary intervention
PG	performance goal
PP	per protocol

Clinical Investigation Plan

Acronym or Abbreviation	Complete Phrase or Definition
PVDF-HFP	Polymer of vinylidene fluoride and hexafluoropropylene
QCA	quantitative coronary angiography
QMI	Q wave myocardial infarction
RCA	right coronary artery
RFR	relative flow reserve
RVD	reference vessel diameter
RX	Rapid Exchange
SAE	serious adverse event
SAP	statistical analysis plan
SCAI	Society for Cardiovascular Angiography and Interventions
SPC	Summary of Product Characteristics
ST	stent thrombosis
STEMI	ST-Elevation MI
TBD	to be determined
TIA	transient ischemic attack
TIMI	thrombolysis in myocardial infarction
TLF	target lesion failure
TLR	target lesion revascularization
TVF	target vessel failure
TVR	target vessel revascularization
UADE	unanticipated adverse device effect
URL	upper reference limit
US	United States
USADE	unanticipated serious adverse device effect

Clinical Investigation Plan

18.0 APPENDIX II: DEFINITIONS

ACC/AHA Classification Scheme of Coronary Lesions: Lesion-Specific Characteristics

Type A Lesions (High Success, >85%; Low Risk)

- | | |
|--|---|
| 
 • Discrete (< 10 mm length) • Concentric • Readily accessible • Nonangulated segment, < 45° • Smooth contour | 
 • Little or no calcification • Less than totally occlusive • Not ostial in location • No major branch involvement • Absence of thrombus |
|--|---|

Type B Lesions* (Moderate Success, 60-85%; Moderate risk)

- | | |
|--|--|
| 
 • Tubular (10-20 mm length) • Eccentric • Moderate tortuosity of proximal segment • Moderately angulated segment, > 45°, < 90° • Irregular contour | 
 • Moderate-to-heavy calcification • Total occlusions < 3 months old • Ostial in location • Bifurcation lesions requiring double guide wires • Some thrombus present |
|--|--|

* Type B1 lesions: One adverse characteristic

* Type B2 lesions: ≥ two adverse characteristics

Type C Lesions (Low Success, <60%; High Risk)

- | | |
|---|--|
| 
 • Diffuse (> 2 cm length) • Excessive tortuosity of proximal segment • Extremely angulated segments > 90° | 
 • Total occlusions > 3 months old • Inability to protect major side branches • Degenerated vein grafts with friable lesions |
|---|--|

ACUTE SUCCESS

Acute Success is classified according to the following definitions:

• **Device Success**

Device success is defined as achievement of a final in-stent residual diameter stenosis of < 50% (by QCA), using only study device(s) without device malfunction. Use of a bail-out study stent is still regarded as device success unless the bail-out study stent has a device malfunction. If QCA %DS is not available, device success will be missing

• **Procedure Success**

Procedure success is defined as achievement of a final in-stent diameter stenosis of < 50% (by QCA) using the assigned device and with any adjunctive devices, without the occurrence of cardiac death, Target Vessel MI (per ARC definition), or repeat coronary revascularization of the target lesion during the hospital stay (up to 7 days if a subject still in the hospital). If QCA %DS is not available, procedure success will be missing.

Clinical Investigation Plan

DEATH (Per ARC Circulation 2007; 115: 2344-2351)

All deaths are considered cardiac unless an unequivocal non-cardiac cause can be established. Specifically, any unexpected death even in subjects with coexisting potentially fatal non-cardiac disease (e.g. cancer, infection) should be classified as cardiac.

Cardiac death:

Any death due to proximate cardiac cause (e.g. MI, low-output failure, fatal arrhythmia), unwitnessed death and death of unknown cause, all procedure related deaths including those related to concomitant treatment.

Vascular death:

Death due to non-coronary vascular causes such as cerebrovascular disease, pulmonary embolism, ruptured aortic aneurysm, dissecting aneurysm, or other vascular cause.

Non-cardiovascular death:

Any death not covered by the above definitions such as death caused by infection, malignancy, sepsis, pulmonary causes, accident, suicide or trauma.

MYOCARDIAL INFARCTION [MI]

1. Peri procedure MI

a. MI per SCAI definition⁴ (J Am Coll Cardiol. 2013; 62(17):1563-70):

defined as the occurrence within 48 hours after either PCI or CABG of either:

- CK-MB above 10 x URL (*determined on a single measurement), OR
- CK-MB above 5 x URL (*determined on a single measurement), PLUS
 - new pathological Q waves in at least 2 contiguous leads or new persistent non-rate related LBBB

In the absence of CK-MB measurements and a normal baseline cardiac troponin (cTn), peri-procedural MI can also be defined as a cTn (I or T) level measured within 48 hours of the PCI rises to ≥ 70 x the local laboratory URL, or ≥ 35 x URL with new pathologic Q-waves in ≥ 2 contiguous leads, or new persistent LBBB.

b. MI per ARC 2 definition⁷ (Circulation 2018; 137, 2635-2650):

For PCI and coronary artery bypass grafting (CABG), within 48 Hours:

Clinical Investigation Plan

Absolute rise in cardiac troponin (from baseline) ≥ 35 times upper reference limit, plus 1 (or more) of the following criteria:

- New significant Q waves or equivalent
- Flow-limiting angiographic complications
- New “substantial” loss of myocardium on imaging

Significant periprocedural myocardial injury:

Absolute rise in cardiac troponin (from baseline) ≥ 70 times upper reference limit.

c. MI per 4th universal definition⁸ (*Circulation* 138, e618-e651, 2018).

Coronary procedure-related MI ≤ 48 hours after the index procedure is arbitrarily defined by an elevation of cTn values > 5 times of the 99th percentile URL in patients with normal baseline values. Patients with elevated pre-procedural cTn values, in whom the pre-procedural cTn level are stable ($\leq 20\%$ variation) or falling, must meet the criteria for a > 5 -fold increase and manifest a change from the baseline value of $> 20\%$. In addition with at least one of the following:

- New ischaemic ECG changes;
- Development of new pathological Q waves;
- Imaging evidence of loss of viable myocardium that is presumed to be new and in a pattern consistent with an ischaemic aetiology;
- Angiographic findings consistent with a procedural flow-limiting complication such as coronary dissection, occlusion of a major epicardial artery or graft, side-branch occlusion-thrombus, disruption of collateral flow or distal embolization.

2. Spontaneous MI: (> 48 h following PCI or CABG): CK-MB $> URL$ or Troponin $> URL$ with baseline value $< URL$

MI after the periprocedural period may be secondary to late stent complications or progression of native disease. Performance of ECG and angiography supports adjudication to either a target or non-target vessel in most cases.

With the unique issues and pathophysiological mechanisms associated with these later events as well as the documented adverse impact on short and long-term prognosis, a more sensitive definition than for periprocedural MI of any elevation of troponin or CKMB above the 99th percentile of the upper range limit (or ULN if URL is not available) is used. All late events that are not associated with a revascularization procedure will be considered simply as spontaneous.

3. Myocardial infarctions will also be adjudicated based on the following classification:

- Q wave MI

Clinical Investigation Plan

Development of new, pathological Q wave on the ECG (≥ 0.04 seconds in duration and ≥ 1 mm in depth) in ≥ 2 contiguous precordial leads or ≥ 2 adjacent limb leads)

- **Non-Q wave MI**

Those MIs which are not Q-wave MI.

All Myocardial infarctions will be adjudicated by CEC by different definitions mentioned above, and also be adjudicated as to their relation to the target vessel

All infarcts that cannot be clearly attributed to a vessel other than the target vessel will be considered related to the target vessel.

STENT THROMBOSIS (Per ARC Circulation 2007; 115: 2344-2351)

- **Timing:**

Acute stent thrombosis*:	0 - 24 hours post stent implantation
Subacute stent thrombosis*:	>24 hours - 30 days post stent implantation
Late stent thrombosis†:	>30 days - 1 year post stent implantation
Very late stent thrombosis†:	>1 year post stent implantation

* Acute/subacute can also be replaced by early stent thrombosis.

† Including "primary" as well as "secondary" late stent thrombosis; "secondary" late stent thrombosis is a stent thrombosis after a target segment revascularization.

- **Categories (Definite, Probable, and Possible):**

Definite stent thrombosis

Definite stent thrombosis is considered to have occurred by either angiographic or pathologic confirmation.

Angiographic confirmation of stent thrombosis*

The presence of a thrombus[†] that originates in the stent or in the segment 5 mm proximal or distal to the stent and presence of at least 1 of the following criteria within a 48-hour time window:

- Acute onset of ischemic symptoms at rest
- New ischemic ECG changes that suggest acute ischemia
- Typical rise and fall in cardiac biomarkers (refer to definition of spontaneous MI)
- Non-occlusive thrombosis
 - Intracoronary thrombus is defined as a (spheric, ovoid, or irregular) non-calcified filling defect or lucency surrounded by contrast material (on 3 sides or within a coronary stenosis) seen in multiple projections, or persistence of contrast material within the lumen, or a visible embolization of intraluminal material downstream.
- Occlusive thrombus
 - TIMI 0 or TIMI 1 intrastent or proximal to a stent up to the most adjacent proximal side branch or main branch (if originates from the side branch).

Clinical Investigation Plan

Pathological confirmation of stent thrombosis

Evidence of recent thrombus within the stent determined at autopsy or via examination of tissue retrieved following thrombectomy.

- * The incidental angiographic documentation of stent occlusion in the absence of clinical signs or symptoms is not considered a confirmed stent thrombosis (silent occlusion).
- † Intracoronary thrombus.

Probable stent thrombosis

Clinical definition of probable stent thrombosis is considered to have occurred after intracoronary stenting in the following cases:

- Any unexplained death within the first 30 days‡
- Irrespective of the time after the index procedure, any MI that is related to documented acute ischemia in the territory of the implanted stent without angiographic confirmation of stent thrombosis and in the absence of any other obvious cause

- ‡ For studies with ST-elevation MI population, one may consider the exclusion of unexplained death within 30 days as evidence of probable stent thrombosis.

Possible stent thrombosis

Clinical definition of possible stent thrombosis is considered to have occurred with any unexplained death from 30 days after intracoronary stenting until end of trial follow-up.

STROKE

An acute symptomatic episode of neurological dysfunction attributed to a vascular cause lasting more than 24 hours or lasting 24 hours or less with a brain imaging study or autopsy showing new infarction.

- Ischemic Stroke: An acute symptomatic episode of focal cerebral, spinal, or retinal dysfunction caused by an infarction of central nervous system tissue.
- Hemorrhagic Stroke: An acute symptomatic episode of focal or global cerebral or spinal dysfunction caused by a non-traumatic intraparenchymal, intraventricular, or subarachnoid hemorrhage.
- Undetermined Stroke: A stroke with insufficient information to allow categorization as ischemic or hemorrhagic.

Note: an event that last < 24 hours may be adjudicated as a stroke if the following treatments were used:

- Pharmacologic, i.e., thrombolytic drug administration, or

Non-pharmacologic, i.e., neurointerventional procedure (e.g., intracranial angioplasty)

REVASCULARIZATION (Per ARC Circulation 2007; 115: 2344-2351)

Target Lesion Revascularization (TLR)

Clinical Investigation Plan

TLR is defined as any repeat percutaneous intervention of the target lesion or bypass surgery of the target vessel performed for restenosis or other complication of the target lesion. All TLR should be classified prospectively as clinically indicated [CI] or not clinically indicated by the investigator prior to repeat angiography. The target lesion is defined as the treated segment from 5 mm proximal to the stent and to 5 mm distal to the stent.

Target Vessel Revascularization (TVR)

TVR is defined as any repeat percutaneous intervention or surgical bypass of any segment of the target vessel. The target vessel is defined as the entire major coronary vessel proximal and distal to the target lesion which includes upstream and downstream branches and the target lesion itself

Non Target Lesion Revascularization (Non-TLR)

Any revascularization in the target vessel for a lesion other than the target lesion is considered a non-TLR.

Non Target Vessel Revascularization (Non-TVR)

Revascularization of the vessel identified and treated as the non-target vessel at the time of the index procedure.

Clinically Indicated [CI] Revascularization (TLR/TVR)

A revascularization is considered clinically indicated if angiography at follow-up shows a percent diameter stenosis $\geq 50\%$ and if one of the following occurs:

- A positive history of recurrent angina pectoris, presumably related to the target vessel;
- Objective signs of ischemia at rest (ECG changes) or during exercise test (or equivalent), presumably related to the target vessel;
- Abnormal results of any invasive functional diagnostic test (e.g., Doppler flow velocity reserve, fractional flow reserve);
- A TLR/TVR with a diameter stenosis $\geq 70\%$ in the absence of the above mentioned ischemic signs or symptoms.

TARGET LESION FAILURE (TLF)

TLF is defined as a composite of all cardiac death, myocardial infarction attributed to target vessel or clinically-indicated TLR.

TARGET VESSEL FAILURE (TVF)

TVF is defined as a composite of cardiac death, MI attributed to target vessel, clinically-indicated TLR, or clinically-indicated TVR, non-TLR.

COVID-19 Relatedness Definitions

The COVID-19 relatedness to an adverse event, is adjudicated by the CEC committee into 3 categories: likely related, possibly related, or not likely related, based on the COVID-19 relatedness definitions that are described on the CEC charter. Please refer to the CEC charter for the COVID-19 relatedness definitions.

IN-STENT

Within the margins of the stent.

Clinical Investigation Plan

Minimal Lumen Diameter (MLD)

Minimum lumen diameter is defined as the shortest diameter through the center point of the lumen. Data are collected from two projections.

PERCENT DIAMETER STENOSIS (%DS)

The value calculated as $100 * (1 - \text{MLD}/\text{RVD})$ using the mean values from two orthogonal views (when possible) by QCA.

REFERENCE VESSEL DIAMETER (RVD)

Reference vessel diameter based on QCA is derived from either the user-defined method using average diameter of proximal and distal healthy segments or the interpolated method.

RESTENOSIS

Re-narrowing of the artery following the removal or reduction of a previous narrowing.

TIMI (THROMBOSIS IN MYOCARDIAL INFARCTION) FLOW GRADES

0. No contrast flow through the stenosis.
1. A small amount of contrast flows through the stenosis but fails to fully opacify the artery beyond.
2. Contrast material flows through the stenosis to opacify the terminal artery segment. However, contrast enters the terminal segment perceptibly more slowly than more proximal segments. Alternatively, contrast material clears from a segment distal to a stenosis noticeably more slowly than from a comparable segment not preceded by a significant stenosis.
3. Anterograde flow into the terminal coronary artery segment through a stenosis is as prompt as anterograde flow into a comparable segment proximal to the stenosis. Contrast material clears as rapidly from the distal segment as from an uninvolved, more proximal segment.

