2.2 Device(s) To Be Used in the Clinical Investigation

2.2.1 Name of the Device(s) Under Investigation

The study device for the SPIRIT 48 study is the ABT NG DES 48, an investigational device, with the following available sizes:

Table 2.2.1-1 ABT NG DES 48 Size Matrix

Stent Design	Product Diameter (mm)	48mm
Small	2.5	X
	2.75	X
	3.0	X
Medium	3.5	X
	4.0	X

The ABT NG DES 48 is manufactured by Abbott.

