3.1 Clinical Investigation Procedures and Follow-up Schedule

A total of up to 107 subjects will be registered in the SPIRIT 48 study. Subjects registered in the study must have exactly one single *de novo* native coronary target lesion (defined in **Section 5.3**), which is eligible to be treated by a single ABT NG DES 48. Planned overlap is not allowed for the treatment of target lesion. If a bailout stent is necessary for the target lesion, a XIENCE family stent with appropriate size (including the ABT NG DES 48) must be used. A non-target lesion, if is located in a different epicardial coronary vessel than the target lesion, is allowed to be treated by stents other than the ABT NG DES 48 per site's standard of care during index procedure. All subjects must be treated with only one ABT NG DES 48.

- Lesions and stent usage: up to two treated lesions, must have exactly one long lesion that is treated by one ABT NG DES 48
 - Single lesion: one *de novo* native coronary artery long lesion (> 32 mm and ≤ 44 mm) as the target lesion, that must be treated a single ABT NG DES 48
 - Two lesions: one target lesion and one non-target lesion, each in different epicardial coronary vessels:
 - Target Lesion: one *de novo* native coronary artery long lesion (> 32 mm and ≤ 44 mm), that must be treated with a single ABT NG DES 48
 - Non-target lesion: one *de novo* native coronary artery lesion, that must be treated by stents other than the ABT NG DES 48 per site's standard of care

A maximum of 40% of subjects with two treated lesions can be registered in the study. At least 50% of the subjects will be registered at US sites.

Each subject will be followed for a two-year period. All subjects will have a hospital or office follow-up visit at 30 days, 6 months, 1 year and 2 years. An office visit is required for 1-year follow-up. All follow-ups must be conducted directly with the subject. Refer to detailed follow-up schedule in **Section 6.5.4**.

Note: If the scheduled visit occurs outside of the allowed window, it is not considered a missed visit/contact. It is a protocol deviation but still considered a completed visit.

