8.6 Multiplicity

8.7 Procedures for Accounting for Missing Data

All analyses will be based on available data with missing data excluded. Any unused or spurious data will be noted as appropriate in the final report.

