1.3 Clinical Investigation Design

The SPIRIT 48 study is a prospective, single-arm, open-label, multi-center clinical investigation to evaluate the safety and effectiveness of the ABT NG DES 48 in the treatment of *de novo* native coronary artery long lesions. Up to 107 subjects will be registered in the study at up to 33 global sites. Subjects registered in the study must have exactly one single *de novo* native coronary target lesion (defined in **CIP Section 5.3**), which is eligible to be treated by a single ABT NG DES 48. Planned overlap is not allowed for the treatment of target lesion. If a bailout stent is necessary for the target lesion, a stent other than the ABT NG DES 48 with appropriate size must be used. A non-target lesion, if is located in a different epicardial coronary vessel than the target lesion, is allowed to be treated by stents other than the ABT NG DES 48 per site's standard of care during index procedure. All subjects must be treated with only one ABT NG DES 48.

- Lesions and Stent Usage: up to two treated lesions, must have exactly one long lesion that is treated by one ABT NG DES 48
 - Single lesion: one *de novo* native coronary artery long lesion (> 32 mm and ≤ 44 mm) as the target lesion, that must be treated with a single ABT NG DES 48
 - Two lesions: one target lesion and one non-target lesion, each in different epicardial coronary vessels:
 - Target Lesion: one *de novo* native coronary artery long lesion (> 32 mm and ≤ 44mm), that must be treated with a single ABT NG DES 48
 - Non-target lesion: one *de novo* native coronary artery lesion, that must be treated by stents other than the ABT NG DES 48 per site's standard of care

A maximum of 40% of subjects with two treated lesions can be registered in the study. At least 50% of the subjects will be registered at US sites.

Each subject will be followed for a two-year period. All Subjects will have a hospital or office follow-up visit at 30 days, 6 months, 1 year and 2 years. An office visit is required for 1-year follow-up. All follow-ups must be conducted directly with the subject.

Statistical Analysis Plan**1.4 Endpoints****1.4.1 Primary Endpoint**

The primary endpoint for this study is target lesion failure (TLF)^a, defined as a composite of the following clinical endpoints at 1-year:

- Cardiac death
- Target Vessel Myocardial Infarction [TV-MI] (MI is per Society for Cardiovascular Angiography and Interventions (SCAI) definition^[1])

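### Device and procedure success are set to missing when QCA stenosis is unavailable, even for a subject already known to have failed

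*Protocol*

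**What the plan says.** Protocol Appendix II (Acute Success) builds both outcomes from conditions that must all hold.

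- **Device success** needs a final in-stent residual stenosis below 50% by QCA, achieved "using only study device(s) without device malfunction". The rule follows: "If QCA %DS is not available, device success will be missing".
- **Procedure success** needs the same stenosis threshold with the assigned device, and no cardiac death, target vessel MI (labelled per ARC) or repeat target lesion revascularization in hospital. The rule follows: "If QCA %DS is not available, procedure success will be missing".

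Protocol 8.7, repeated in SAP 2.9, says: "All analyses will be based on available data with missing data excluded". Protocol 8.1 and SAP 2.1 and 2.3.3 analyze acute success in all registered subjects with an attempted ABT NG DES 48 implant. Under Protocol 5.4 registration happens once the stent starts to pass the guide catheter tip, so an undelivered stent still counts. SAP 2.2.2 reports the rates with exact Clopper-Pearson 95% intervals.

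On MI, footnote d (Protocol 4.3) and footnote b (SAP 1.4.3) are attached to the headings that list acute success, and both specify SCAI. Appendix II writes out peri-procedural MI criteria for SCAI, ARC 2 and the 4th universal definition, but none labelled plain ARC.

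**The concern.** When every condition is required, one observed failure settles the outcome whatever the QCA would have shown. A subject who dies of a cardiac cause before a final film can be read is a procedure failure with certainty. The rule as written calls that subject missing, and the missing-data sections then remove the subject from the denominator. This defeats the purpose of an all-attempts population, which is to keep failed attempts in the count. At stake is a small overstatement of the device and procedure success rates and their lower confidence limits.

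The MI label raises a second, smaller problem. Appendix II and the footnotes cannot both govern procedure success. The in-hospital target vessel MI that counts toward TLF may therefore differ from the one that counts against procedure success. The direction cannot be determined, because the plain ARC criteria are not given.

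**Working it through.** **Plan's own figure.** There is none to reproduce: the documents give no expected rate for device or procedure success and no expected number of missing QCA readings. Every count below except N is an assumption.

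**Inputs.** N = 107 attempts, the maximum registration, with one target lesion each (Protocol 3.1 and 5.6). Let f be known failures without QCA, g other failures with QCA, and m true successes without QCA. The m subjects are missing under either rule.

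**Formulas.** Successes counted: s = 107 − f − g − m.

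- Current rule: s / (107 − f − m)
- Known failures counted: s / (107 − m)
- Difference: s·f / [(107 − f − m)(107 − m)]. This is never negative, and is zero when f = 0.

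**Results**, with Clopper-Pearson 95% limits in brackets:

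| f, g, m | Current rule | Known failures counted | Difference (points) |
|---|---|---|---|
| 0, 0, 0 | 107/107 = 100% (96.6, 100) | 107/107 = 100% (96.6, 100) | 0 |
| 1, 0, 0 | 106/106 = 100% (96.6, 100) | 106/107 = 99.1% (94.9, 99.98) | 106/(106×107) = 0.93 |
| 1, 5, 0 | 101/106 = 95.3% (89.3, 98.5) | 101/107 = 94.4% (88.2, 97.9) | 101/(106×107) = 0.89 |
| 1, 5, 5 | 96/101 = 95.0% (88.8, 98.4) | 96/102 = 94.1% (87.6, 97.8) | 96/(101×102) = 0.93 |
| 0, 5, 5 | 97/102 = 95.1% (88.9, 98.4) | 97/102 = 95.1% (88.9, 98.4) | 0 |

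The lower limit moves somewhat more than the rate: by 1.68 points (96.58 − 94.90) in the second row and 1.14 (89.33 − 88.19) in the third. The last row shows that true successes with no usable QCA create no difference between the rules.

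**Who is affected.** Protocol 6.2.5 requires a final target lesion film in all subjects. A failure with a readable film is scored as a failure under either rule, so what remains is a known failure with no usable final film, for instance death or emergency surgery before it is taken. A failed delivery that leaves no stent in place depends on how the trigger is read:

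- The trigger says QCA %DS. Appendix II computes %DS from minimal lumen diameter and reference diameter, which needs no stent. On this reading a failed delivery with a readable film has a value and is not missing.
- The criterion itself is in-stent stenosis, and Appendix II defines in-stent by the margins of the stent. On this reading a failed delivery has no value and drops out even with a good film.

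The text does not choose between them.

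**The case against.** The strongest case against is that this is a drafting gap with little reach. Acute success is descriptive: SAP 2.11 confines formal testing to the primary endpoint. The final film is mandatory. The underlying events also appear elsewhere: TLF, death, MI and revascularization in hospital (SAP 1.4.2 and 1.4.3), adjudicated events and adverse device effects in all registered subjects (SAP 3.2), early termination reasons (SAP 3.3) and device deficiencies (Protocol 7.3.3). Blacked-out text follows the population statements in Protocol 8.1 and SAP 2.1 and could hold a scoring rule. All of this stands, and it limits the severity. It does not repair Appendix II, whose visible rule has no exception.

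A reader might infer three stronger things, none of which the documents support.

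- **That all failed deliveries leave the denominator.** This follows only if the trigger means in-stent %DS, which is left open.
- **That the total effect of missing QCA must be upward.** That holds only for the known failures that are dropped. True successes without QCA are a separate matter, unchanged by either rule.
- **That a non-study bail-out stent in the target lesion is already a device failure.** Protocol 2.2.1 says: "The study device for the SPIRIT 48 study is the ABT NG DES 48, an investigational device". Appendix II adds: "Use of a bail-out study stent is still regarded as device success unless the bail-out study stent has a device malfunction". For bail-out, Protocol 3.1 says "a XIENCE family stent with appropriate size (including the ABT NG DES 48) must be used", while SAP 1.3 says "a stent other than the ABT NG DES 48 with appropriate size must be used". Protocol 3.1 also limits each subject to one ABT NG DES 48, and Protocol 10.6 makes implanting more than one a major deviation. Until these agree, the meaning of a bail-out study stent is unsettled and its scoring cannot be fixed.

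On MI, one can argue that Appendix II is the more specific text and that ARC was intended. The documents establish a conflict, not which side was meant.

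**Conclusion.** The point holds in a narrow form. Followed exactly, the plan turns certain failures into missing values and excludes them from an all-attempts denominator. Compared with counting them, the reported rate can only go up: about 0.9 points per such subject at N = 107, and nothing if there are none. How many to expect cannot be taken from the documents. The primary TLF endpoint, alpha and power are unaffected.

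The MI conflict for procedure success is real, but its size cannot be computed. The bail-out conflict is a separate issue and is only flagged here.

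Severity is minor. Confidence is moderate to high on the readable text, with the reservation that redacted SAP text may contain a further rule.

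**What to change.** In SAP 2.3.3 now, and in Appendix II at the next amendment:

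1. Score as a failure, whether or not QCA exists, any subject with an observed failure on a criterion that does not depend on QCA. For device success: no study stent implanted, or a disqualifying malfunction. For procedure success: assigned device not implanted, or cardiac death, target vessel MI or repeat target lesion revascularization in hospital.
2. Keep missing for subjects who meet every other criterion but lack QCA %DS, and report their number.
3. State whether the trigger is in-stent %DS.
4. Name one MI definition for procedure success. SCAI would agree with both footnotes.
5. If redacted text holds a scoring or denominator rule for acute success, make it agree.

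Scoring of a target lesion bail-out stent must wait until the sponsor has reconciled Protocol 3.1 (including its one-stent sentence), Protocol 10.6, SAP 1.3 and the bail-out sentence in Appendix II.

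The cost is wording. No new data are needed, since Appendix II already has the CEC adjudicate every MI under the listed definitions, SCAI among them. Changing Appendix II is a protocol amendment with ethics committee handling (Protocol 10.3 and 12.1), so it can wait for one needed anyway. Reported success rates may come out slightly lower.
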